4.8 Data Confidentiality Plan

Patients registered in this protocol will be de-identified by using a unique identifier number that is automatically generated in BMTWeb, linkage to patient sensitive information is not possible outside BMTWeb.

Access to the database is only available to individuals within the department and with authorize access. Data gathered for this study will not be reused or disclosed to any other person or entity, or for other research.

5.0 Evaluation During Study

5.1 Disease Assessment Prior to Start of Pacritinib (baseline):

- a) Patient medical history and physical examination including measurement of liver and spleen size by physical examination or imaging (MRI or CT or ultrasound if possible) with addition of marrow-specific MRI sequences.
- b) CBC, differential and platelet count
- c) Bone marrow aspiration and biopsy
- d) Chemistry panel
- e) Serology for CMV, HBV, HCV and HIV
- f) B-HCG in women of childbearing potential
- g) 2 D echo, EKG
- i) Pulmonary function tests with DLCO
- j) Chest x-ray
- k) MF symptoms questionnaire (Appendix D.)
- I) Fact BMT questionnaire (Appendix E.)
- m) Blood for immunological profile if patient agrees to consent to optional study.

5.2 Follow up each month while on Pacritinib:

Patients will come to MDACC once each month to pick-up the next month's Pacritinib and have the following done. The monthly visits will continue as long as patient is taking Pacritinib.

- a) Medical history and physical examination
- b) CBC, differential and platelet count
- c) Chemistry panel
- d) EKG

Cycle 1 only: Day 14 (+/- 2 days) CBC, differential and platelet count and chemistry panel. These can be drawn locally and results sent to MDACC. The PI/treating physician must review outside lab results, determine clinical significance, sign and date the outside lab results.

Cycle 1 only: During week 2, study personnel will call patient about any new symptoms.

Patients treated on this protocol may require supportive care treatment (concomitant medications). These medications are considered standard of care and have no scientific contribution to the protocol; therefore no data will be captured on various medications needed or their side effects.

5.3 Within about 7 days after completion of Pacritinib (but before transplant):

- 1) Physical examination including measurement of liver and spleen size by physical examination or imaging (MRI or CT or ultrasound if possible).
- 2) EKG
- 3) Bone marrow aspiration and biopsy

5.4 Post-transplant Evaluations:

- 5.4.1 Post-transplant evaluations will follow our standard practice and are done to monitor engraftment and disease status.
- 5.4.2 Additional post-transplant follow-up specific to this study at approximately 1, 3, 6, and 12 months post-transplant:
 - 1) At around 3 months:
 - Measurement of liver and spleen size by physical examination or imaging (MRI or CT or ultrasound if possible).
 - b) Bone marrow aspiration and biopsy

At around 12 months:

- a) Repeat measurement of liver and spleen size, if liver and spleen were still enlarged at 3 months post-transplant.
- b) Bone marrow biopsy aspiration and biopsy
- 2) Blood for immunological profile if patient agrees to consent to optional study.
- 3) MF symptoms questionnaire (Appendix D.)
- 4) Fact BMT questionnaire (Appendix E.)
- 5) Participant Follow-up Assessment questionnaire (Global Impression of Change Scale, Appendix F.)

5.5 Correlative Research Studies (Optional):

60 cc of blood (5 green top tubes and 1 purple top tube) will be collected before the first dose of pacritinib, after the last dose of pacritinib (before transplant), and at approximately 1, 3, 6, and 12 months post-transplant.

This research blood will be sent to [name] laboratory at MD Anderson. Studies to be conducted are described in Section 2.4.

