Pacritinib, a Jak2/Flt 3 inhibitor, has activity in myeloid and lymphoid malignancies. Currently it is in Phase 3 studies in patients with myelofibrosis. Details of this molecule are in the attached investigator brochure and a brief summary follows. It is a potent selective inhibitor of mutant as well as normal Jak2 kinase. Preclinical studies showed its activity in suppressing Jak 2 mediated tumors. PK studies in clinical trials showed slow absorption (Tmax 4-6 hours) and dose related increase in systemic exposure up to 400 mg per day. Terminal elimination half-life was 47 hours. Food did not impair absorption. At 100 mg/day dose steady state levels exceeded IC50 values for inhibition of Jak2/Flt3 kinase. Phase I studies identified 400 mg daily as dose for further studies. Dose limiting toxicity included grade 3 QTc prolongation, grade 3 diarrhea and grade 2 dizziness and blurred vision. Most common adverse events occurring in more than 20% were diarrhea, nausea, vomiting, constipation, dyspnea, fatigue and edema. Most events were mild to moderate severity. Only grade 3 or higher adverse event occurring in more than 10% of patients were anemia or thrombocytopenia (16%). MRI showed ≥ 25% spleen volume reduction in 55% of patients. An improvement in all symptoms relevant to myelofibrosis was seen. Thus, Pacritinib is very safe and highly effective therapy for patients with myelofibrosis and we would like study its role pre-transplant to improve transplant outcomes.

Correlative Research Studies (optional):

To evaluate the effect of the JAK2 inhibitor Pacritinib on immune recovery and graft-versus-host disease post-transplant

Janus kinase-2 (JAK2) conveys receptor-binding signals by several inflammatory cytokines, via phosphorylation of STAT3. Selective inhibition of JAK2 was shown to induce tolerance to allo-antigens, while preserving de novo responses to pathogens 48. Selective JAK2 inhibition was also shown to preserve Treg numbers through preservation of the IL-15/JAK3/pSTAT5 pathway.

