Signaling through IFN γ -receptor, mediated by JAK1/JAK2 and STAT1, has been shown to result in increased surface expression of CXCR3, a key chemokine receptor involved in T-cell trafficking to sites of inflammation. A recent study in a murine model of GVHD, showed that pharmacologic inhibition of IFN γ R signaling with inhibitors of JAK1/JAK2 resulted in decreased expression of CXCR3 associated with reduced GVHD, mediated by altered trafficking of effector T cells to GVHD target organs, ⁴⁹ providing another mechanism through which selective JAK2 inhibition could influence GVHD.

We *hypothesize* that the Jak 2 inhibitor, Pacritinib will reduce the risk of GVHD in patients with myelofibrosis undergoing allogeneic stem cell transplantation, resulting in improved survival.

To test this hypothesis we propose the following aims:

Aim 1: To determine how Pacritinib affects the balance of Treg/Th1/Th2/Th17 cells. T cells collected at multiple time points before and during therapy (as outlined below) will be activated via CD3/TCR and CD28 ligation and differentiated according to their cytokine profile into Th1 (CD4+IFN- γ +), Th2 (CD4+IL-4+), Th17 (CD4+IL-17+) and Tr1 (CD4+IL-10+). Naturally occurring Tregs will be defined as CD4+CD25hiFoxp3+CD127lo.

Aim 2: To determine how Pacritinib influences the expression of chemokine receptors on the surface of T cells, including CXCR2, CXCR3, CXCR4, CXCR5, CCR3, CCR4, CCR5, CCR6,

CCR7, and CCR9

Aim 3: To determine how Pacritinib influences the pathogen-specific immune responses.

We will conduct analyses of T cell phenotype, estimate antigen-specific T cell precursor frequencies (by intracellular cytokine flow cytometry and peptide/dextramer staining) and determine antigen-specific cytokine production capacity (cytokine bead array assay). We will perform:

- Immunophenotypic recovery of naive, stem-like memory, central and effector memory CD4+ and CD8+ T cells, using a 10 color flow cytometry panel (CD3, CD4, CD8, CD45RA, CD45RO, CCR7, CD62L, CD95, IL-7Rα, IL-2Rα);
- 2) The number and function of recovering CMV, T cells capable of responding functionally to in vitro stimulation with overlapping pools of peptide by intracellular cytokine detection. ^{3,5,6}

Aim 4: To determine how Pacritinib influences the phenotype and function of dendritic cells (DCs).

We will characterize DC subsets in PB collected at multiple time points before and during therapy (as outlined below) by:

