4.0 Treatment Plan

4.1 The investigational agent for this study is Pacritinib.

- 4.1.1 Patients will start Pacritinib 200 mg po bid.
- 4.1.2 Patients can proceed to transplant after 60 days of starting Pacritinib but not more than 180 days.
- 4.1.3 Pacritinib will be stopped 21 days prior to starting preparative regimen for SOC Allo TP.
- 4.1.4 If for whatever reason a patient cannot pursue or receive SOC Allo TP, they will be able to continue treatment with Pacritinib until there is evidence of disease progression.
- 4.1.5 A patient will still be able to proceed to SOC ALLO TP if for any reason they cannot complete 60 days of treatment prior to transplant.
- 4.1.6 If a patient vomits or misses a dose, will continue treatment with the next scheduled dose. Missed doses and reason for non-compliance will be recorded.
- 4.1.7 Every effort should be made to avoid CYP3A4 inducers or inhibitors (see Appendix H) while patients are on pacritinib. If concomitant therapy with CYPsA4 inhibitors or inducers is medically necessary and there are no available or suitable substitutes, this should be documented in the patient's medical record and extreme caution taken with their continued use during the study duration.
- 4.1.8 Patients will document compliance of taking medication on a patient diary.

4.2 Treatment Interruption:

Safety parameters including AEs, hematology, and serum chemistry will be monitored according to the protocol. Pacritinib treatment may be withheld for up to 4 weeks due to drug-related toxicities. A longer recovery period may be allowed based on the toxicity, but must be agreed upon between the investigator and medical monitor. After treatment interruption, patients may resume the pacritinib treatment at the same dose level or at a reduced dose level. No dose re-escalation is allowed.

4.3 Pacritinib Dose Management Guidelines for Pacritinib-Related Nonhematologic Toxicities:

- 4.3.1 A maximum of 2 dose reductions is allowed. The first dose reduction will be a 100 mg reduction from the original dose. The dose will be reduced to 200 mg Q AM and 100 mg Q PM
- 4.3.2 The second dose reduction will be another 100 mg reduction and the dose will be reduced to 100 mg BID.
- 4.3.3 Once the dose is reduced, no re-escalation is allowed.
- 4.3.4 Dose management for nonhematologic toxicities is summarized in Table 3.

Table 3 Treatment Toxicity and Dose Management: Pacritinib-Related Nonhematologic Toxicities		

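### Aims 1 and 4 of the optional immune substudy call for cells taken during therapy, but no research draw falls while the patient takes pacritinib, and the one draw between last dose and transplant has no time window

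*Combined protocol and SAP*

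**What the plan says.** The aims are in section 2.0 under Correlative Research Studies. For Aim 1, T cells "collected at multiple time points before and during therapy (as outlined below) will be activated via CD3/TCR" and CD28 ligation. For Aim 4, "We will characterize DC subsets in PB collected at multiple time points before and during therapy (as outlined below) by" subset and co-stimulatory markers. Aims 2 and 3 also ask how pacritinib influences immune cells or responses, but name no time points.

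The only schedule that follows is section 5.5. Research blood (60 cc each time) is taken "before the first dose of pacritinib, after the last dose of pacritinib (before transplant), and at approximately 1, 3, 6, and 12 months post-transplant".

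The visit lists agree with 5.5. Immunological blood appears at baseline (5.1, item m) and after transplant (5.4.2). Section 5.2 sets monthly on-drug visits: "Patients will come to MDACC once each month to pick-up the next month's Pacritinib and have the following done". The list there is history and examination, blood count, chemistry and EKG. Section 5.3, within about 7 days after pacritinib is completed, lists examination or imaging, EKG and marrow. Neither includes research blood.

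Two further statements fix the timing. Section 4.1.3: "Pacritinib will be stopped 21 days prior to starting preparative regimen for SOC Allo TP". Section 2.0, Pacritinib: "Terminal elimination half-life was 47 hours".

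Section 6.0, Secondary Analyses, plans mixed models or other suitable models for change over time in cell subsets and cytokines. It gives no draw window, no term for time since last dose and no contrast designated as the pacritinib effect.

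**The concern.** The mechanisms that motivate the substudy (JAK2/STAT3 signalling, CXCR3 expression, preservation of regulatory T cells) are consequences of JAK inhibition. The direct way to see them in patients is to compare each patient's own cells before pacritinib with the same patient's cells under it. The schedule does not secure that comparison.

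The draw after the last dose is the only one that separates pacritinib from the transplant, and its exposure is left to scheduling. If some patients are sampled within a day or two and others two or three weeks later, a reversible effect will tend to be diluted, and the estimate will depend on the mix of draw days. A null result could then mean no effect or merely late draws.

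The post-transplant samples cannot fill the gap. They follow washout, conditioning, donor-cell infusion and GVHD prophylaxis, in a single-arm study with no concurrent patients who went without pacritinib.

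**Working it through.** **Step 1. Count the draws by exposure (section 5.5).**

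| Draw | Exposure |
|---|---|
| Before first dose | Off drug (baseline) |
| After last dose, before transplant | Washout of unspecified length |
| About 1, 3, 6 and 12 months post-transplant | Off drug, after conditioning and graft |

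Draws scheduled while the patient takes pacritinib: 0 of 6. Sections 5.2 and 5.3 add none.

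**Step 2. Bound the second draw.** Its earliest time is straight after the last dose. Its only stated upper limit is transplant. Under 4.1.3, conditioning starts 21 days after pacritinib stops, so day 21 is reachable. A draw during conditioning would be later still, and would also be affected by the conditioning drugs.

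**Step 3. Convert to exposure.** The plan states no figure for exposure at the draw, so there is none to reproduce. Half-lives elapsed = days × 24 / 47; fraction remaining = 0.5^(half-lives). This assumes simple exponential decay at the terminal half-life.

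| Days since last dose | Half-lives | Drug remaining |
|---|---|---|
| 0 | 0 | 100% |
| 2 | 48/47 = 1.0 | 49% |
| 4 | 96/47 = 2.0 | 24% |
| 7 | 168/47 = 3.6 | 8.4% |
| 14 | 336/47 = 7.1 | 0.7% |
| 21 | 504/47 = 10.7 | 0.06% |

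Two patients sampled in full compliance could differ in relative exposure by more than 1,000-fold (2^10.7).

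**Step 4. Ask how long a post-dose draw might still show inhibition.** Section 2.0 says steady-state levels at 100 mg/day exceeded the IC50 for JAK2/FLT3. The starting dose in 4.1.1 is 200 mg twice daily, or 400 mg/day. If exposure is proportional to dose, the fall from the 400 to the 100 mg/day level takes log2(400/100) = 2 half-lives, 2 × 47 / 24 = 3.9 days. From the lowest dose level (200 mg/day, 4.3.6) it takes 1 half-life, 47 / 24 = 2.0 days. So a draw within about 2 to 4 days may still be an exposed sample. By day 7, 8.4% of 400 mg/day corresponds to about 34 mg/day, below that reference level.

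**Step 5. Check whether the analysis could repair it.** Each patient has only one post-dose, pre-transplant draw. Any adjustment for time since last dose would therefore rest on comparisons between patients sampled on different days, not on change within a patient, and the plan specifies no such adjustment.

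**The case against.** Several points on the other side are sound and limit what can be said.

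- A reader might infer that the pacritinib effect cannot be read at all, or that the aims are unanswerable. The documents do not support that. A draw on or soon after the last dose complies with 5.5 and, by step 4, may still show host cells under inhibition. The plan permits an informative sample; it does not ensure one.
- A reader might extend the contradiction to all the immune aims. The wording about sampling during therapy is explicit only for Aims 1 and 4. Aim 3 speaks of recovering T cells, which fits the post-transplant draws, and the substudy's heading is immune recovery and GVHD after transplant.
- A reader might say the post-transplant cells never met the drug. That presumes complete donor replacement. The protocol plans chimerism testing and does not presume its result.
- *Therapy* could mean the whole pacritinib-plus-transplant strategy, as section 1.0 uses it. The definition of active treatment as receiving pacritinib sits in the adverse-event section. But the broader reading does not rescue aims that ask what pacritinib does: in a single arm, post-transplant samples cannot isolate it.
- Time since last dose should be largely derivable, because patients keep a dosing diary (4.1.8), and section 6.0 leaves room for other models. This makes the repair cheap. It does not make exposure uniform.
- The washed-out pre-transplant sample has its own value as a description of the host entering transplant. Moving it is a real loss.

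**Conclusion.** The inconsistency between the aims in section 2.0 and the schedule in 5.5 stands for Aims 1 and 4. The plan contains no on-drug research draw, and the sole pre-transplant draw after dosing can represent anything from 100% to about 0.06% of drug remaining at the start of conditioning. The effect of pacritinib on host T cells and dendritic cells therefore cannot be reliably or uniformly estimated, and no contrast or time-since-dose term is specified to deal with that.

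The percentages rest on simple exponential decay at 47 hours. The 2 to 4 day period of possible continued inhibition also assumes dose-proportional exposure. The scheduling contradiction itself needs neither assumption.

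The reach is limited. The substudy is optional, objective 1.5 (immune recovery) is still served by the 1, 3, 6 and 12 month samples, and neither the primary endpoint nor the 21 evaluable patients is touched. It is worth correcting because samples not taken on drug cannot be recovered later.

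**What to change.** Reconcile the aims in section 2.0 with 5.2, 5.3 and 5.5:

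1. In 5.5, time the second research draw to the last monthly visit in 5.2 while the patient is taking pacritinib, or to the last dosing day.
2. Record the time from last dose to draw. This also identifies a visit that happens to fall in a treatment interruption.
3. In section 6.0, name the paired change from baseline to the on-drug draw as the analysis for the pacritinib-effect aims, and report the 1, 3, 6 and 12 month samples as immune recovery.

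The cost is a schedule amendment. Patients already attend and give blood each month, so using a 5.2 visit adds no visit, no draw and no volume. The last-dosing-day option may need its own attendance if it does not coincide with a visit. The downside is losing the washed-out pre-transplant sample, unless the sponsor keeps it as one additional 60 cc draw with a fixed window. The 5.3 visit is an available anchor.

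If no on-drug draw is to be taken, Aims 1 and 4 should be reworded to what the schedule can show: the state of host cells after pacritinib has stopped, and recovery after transplant.

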6.0 Statistical Considerations

General

This will be a single-arm, Phase II study of pacritinib, fludarabine, and busulfan as a preparative

regimen in allogeneic stem cell transplantation in patients with myelofibrosis. The primary endpoint is progression-free survival (PFS) in patients undergoing matched related or at least 7/8 matched unrelated donor transplant. We will enroll at least 21 evaluable patients, defined as patients who undergo transplant with a matched related or at least 7/8 matched unrelated donor. Patients who do not have a suitable related or unrelated donor will come off study and may receive a transplant from a haploidentical donor. For this reason and because some patients may decide not to undergo transplant after starting the drug, we may need to enroll up to 40 patients to ensure that 21 are evaluable for our primary endpoint.

Endpoints

6.1 Primary End Point (Progression-Free Survival):

Progression-free survival is defined as the time of stem-cell transplant to the time of death or disease progression.

6.2 Secondary End Points:

Neutrophil Engraftment is defined as a sustained ANC \geq 0.5 x 10 $^{\circ}$ /L for 3 consecutive days and evidence of donor chimerism by D+28 (the first chimerism study will be done 3-4 weeks post-transplant).

Platelet Engraftment is defined as a sustained first of three consecutive laboratory values of platelet $\geq 20x109/L$ with no platelet transfusions administered for 7 consecutive days.

Non-relapse mortality is defined as death without disease progression.

Liver response will be defined by the change in the size of the liver measured below the coastal margin in the mid-clavicular line by palpitation.

Spleen response will be defined by the change in the size of the spleen measured below the coastal margin in the mid-clavicular line by palpitation.

Quality of life will be measured by the QOL FACT BMT.

Symptom score will be measured by the MPD symptom score.

Immune recovery will be measured by various cell subsets and cytokine levels.

Primary Graft Failure is defined as failure to achieve an ANC \geq 0.5 x 10 $^{\circ}$ /L for 3 consecutive days by day 28, with <10% cellularity on bone marrow biopsy and no evidence of donor chimerism.

Secondary graft failure is defined as a sustained declined of ANC <0.5 x 10°/L for 3 consecutive days after initial documented engraftment with no evidence of disease progression.

Complete remission is defined as per response criteria defined by European Myelofibrosis network (Appendix G.).

Relapse will be recorded by the day of detection.

Overall Survival is defined as the interval between day of transplant and day of death.

Sample Size and Power

The historical 1-year PFS rate in this population is 61%. Our goal is to improve this to 80%. We expect to enroll patients over a 3-year period and follow all patients for 1 year after enrollment is complete. Under these assumptions, assuming exponentially -distributed PFS times, and using a one-sided exponential MLE test with a 5% Type I error rate, we will need 21 patients to have 80% power to detect an increase in 1-year PFS to 80%. We will provide the 1-year PFS rate along with a corresponding 95% interval and test the hypothesis that it is greater than 61% using an exponential MLE test. Only patients who undergo transplant with a matched related or at least 7/8 matched unrelated donor will be include in this analysis.

Secondary Analyses

We will use the Kaplan-Meier method to estimate the distribution of secondary time-to-event (TTE) endpoints overall survival, time to neutrophil engraftment, and time to platelet engraftment. We will use Cox regression analysis will be used to assess the association between TTE endpoints (including PFS) and clinical and disease covariates of interest. We will assess the cumulative incidence of non-relapse mortality (NRM) and disease relapse in a competing risks framework and use the method of Fine and Gray to fit regression models to these endpoints.

Liver and spleen response to pacritinib will be measured by the change in the size of each organ measured below the coastal margin in the mid-clavicular line by palpation and imaging.

Quality of life (QOL) will be assessed using the QOL FACT BMT, and symptom score will be assessed by the MPD symptom score. Changes in these over time will be analyzed by a generalized linear mixed model (GLMM) approach to account for intra-patient correlation.

For the immune studies, various cell subsets and cytokine levels will be assessed at several timepoints. GLMM or other appropriate statistical models will be fit to assess changes over time in these parameters and relationships with other endpoints.

We will use descriptive statistical methods to tabulate safety parameters such as the rate of adverse events. Only patients who undergo transplant with a matched related or at least 7/8 matched unrelated donor will be include in these analyses.

We will separately summarize safety and other data for patients who receive pacritinib but who do not undergo stem cell transplant.

We will perform a descriptive statistical analysis of the Participant Follow-up Assessment questionnaire (Global Impression of Change Scale, Appendix F.) data collected at approximately 1, 3, 6, and 12 months post-transplant.

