CTCAE Toxicity Grade	Management/ Action	
1 or 2	No change.	
3	 Hold treatment. If the toxicity resolves to grade ≤ 1 or to the baseline grade within 7 days, treatment may be resumed at the same level or the next lower dose, at the discretion of the investigator after discussion with the sponsor. Toxicity that does not resolve to grade ≤ 1 or to the baseline grade within 7 days requires dose reduction to the next lower dose level. 	
4	 Hold treatment. If the toxicity resolves to grade ≤ 1 or to the baseline grade within 7 days, treatment may be resumed, but dose will be reduced by one dose level from the level at which the toxicity was observed. If grade 4 toxicity occurs at the lowest dose of 200 mg/day, the patient should be discontinued from the study. 	

4.3.6 The lowest dose of pacritinib used in the study will be 200 mg/day. If toxicity persists despite dose reduction to 200 mg/day, the patient should be discontinued from treatment.

4.4 Dose Management Guidelines for Hematologic Toxicities:

- 4.4.1 Myelosuppression is an expected event in patients with MF. However, myelosuppression with associated complications such as fever, infection, or bleeding or myelosuppression that worsens during treatment (based on local laboratory values) must be reported as an AE.
- 4.4.2 Patients with myelosuppression may receive supportive care including transient use of granulocyte colony stimulating factor for the treatment of febrile neutropenia and transfusion as clinically indicated.
- 4.4.3 Patients receiving pacritinib are not allowed to receive hematopoietic growth factors such as erythropoietin for the treatment of anemia.
- 4.4.4 Patients with clinically significant worsening of myelosuppression (as judged by the investigator and based on local laboratory values) for more than 7 days or myelosuppression associated with infection or bleeding should have pacritinib dosing interrupted. Pacritinib may be restarted at a reduced dose once the toxicity has resolved to grade ≤ 2 or to the baseline grade and the complications of myelosuppression such as infection or hemorrhage have resolved.

4.5 Allogeneic graft:

Peripheral blood (PB) or bone marrow (BM) progenitor cells may be used in this study peripheral blood will be preferred.

4.6 **Preparative Regimen**:

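### No cumulative count of pacritinib-related death, permanent discontinuation or toxicity-blocked transplant triggers a mandatory review, and patients who lose transplant this way are by implication replaced and enter neither PFS nor OS

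*Combined protocol and SAP*

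**What the plan says.** **Enrolment.** Section 6.0 (General) asks for at least 21 evaluable patients. Evaluable means transplanted from a matched related donor, or from an unrelated donor matched at 7/8 or better. It adds: "we may need to enroll up to 40 patients to ensure that 21 are evaluable for our primary endpoint". The two reasons given for the margin are lack of a suitable donor and a patient's decision against transplant. Toxicity is not named.

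**Endpoints.** Section 6.1: "Progression-free survival is defined as the time of stem-cell transplant to the time of death or disease progression". Section 6.2: "Overall Survival is defined as the interval between day of transplant and day of death".

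**Drug phase.** Section 4.1.2: "Patients can proceed to transplant after 60 days of starting Pacritinib but not more than 180 days". Section 4.1.3: "Pacritinib will be stopped 21 days prior to starting preparative regimen for SOC Allo TP". Under 4.1.4, patients who cannot be transplanted may stay on drug: "they will be able to continue treatment with Pacritinib until there is evidence of disease progression". Section 4.1.5 separates stopping early from losing transplant: "A patient will still be able to proceed to SOC ALLO TP if for any reason they cannot complete 60 days of treatment".

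**Toxicity controls.** Sections 4.2 to 4.4 govern holds, dose reductions and discontinuation for the individual patient; 4.3.6, for example: "If toxicity persists despite dose reduction to 200 mg/day, the patient should be discontinued from treatment". Section 7.1 lets the PI remove a patient for unacceptable toxicity. Section 8.0 sends SAEs individually to the IND Office, IRB, drug company and FDA.

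**Safety analysis.** Section 6.0 (Secondary Analyses) plans descriptive tables, with a separate summary for patients who take pacritinib and are not transplanted. No interim use, threshold or action is attached to either.

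**The concern.** Pacritinib is the only investigational component, and it is given before a potentially curative transplant. The harm that matters most in that phase is a drug-related death, or toxicity that costs the patient the transplant. Neither can appear in PFS or OS, because both clocks start at transplant. Such a patient is also not evaluable, so enrolment continues until 21 others are transplanted or 40 have entered. The remaining controls work one patient at a time. They can prompt someone to look at the whole series, but no stated number of events obliges anyone to do so while patients are still being entered.

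**Working it through.** **1. The plan's own figures.** With 21 evaluable among at most 40, up to 40 - 21 = 19 patients (19/40 = 47.5%) may be non-evaluable. The 21 itself is not in dispute. For 1-year PFS of 61% against 80%, one-sided 5%, 80% power, 3 years of accrual and 1 year of follow-up, the hazard-scale exponential formula gives 22.1. Simulated power at 21 for the log-hazard test is 0.818.

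**2. How much toxicity loss the enrolment margin can absorb.** The documents give neither loss rate, so both are assumed. Let q be loss for donor or choice and t the chance that pacritinib toxicity prevents transplant, taken as independent.

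- Chance that a patient is evaluable: p = (1-q)(1-t). For q = 0.20, t = 0.20: 0.80 x 0.80 = 0.64.
- Chance of reaching 21 within 40: P(Bin(40, p) >= 21).
- Mean enrolment: mean of the smaller of 40 and the number needed for 21 evaluable. Mean with blocking toxicity: mean enrolment x t.

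| q | t | p | P(reach 21) | Mean enrolled | Mean with blocking toxicity |
|---|---|---|---|---|---|
| 0.20 | 0 | 0.80 | >0.999 | 26.2 | 0 |
| 0.20 | 0.10 | 0.72 | 0.997 | 29.2 | 2.9 |
| 0.20 | 0.20 | 0.64 | 0.952 | 32.7 | 6.5 |
| 0.20 | 0.30 | 0.56 | 0.729 | 36.3 | 10.9 |
| 0.40 | 0.10 | 0.54 | 0.638 | 37.1 | 3.7 |
| 0.40 | 0.20 | 0.48 | 0.340 | 38.8 | 7.8 |
| 0.40 | 0.30 | 0.42 | 0.118 | 39.7 | 11.9 |

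The last column includes patients who would also have missed transplant for another reason. Multiplying by 1-q leaves losses due to toxicity alone: 2.3, 5.2 and 8.7 in the q = 0.20 rows.

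**3. An illustrative boundary.** For a limit L on the rate of the counted events, take a Beta(2L, 2(1-L)) prior and the smallest count with P(rate > L) of at least 0.90.

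- L = 0.20: 5/10 (0.971), 7/20 (0.923), 10/30 (0.946).
- L = 0.10: 3/10 (0.933), 5/20 (0.959), 6/30 (0.931).

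Exact binomial pause probability. The first figure uses 10 and 20 treated; the second adds 30, which may not be reached.

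| True rate | L = 0.20 | L = 0.10 |
|---|---|---|
| 5% | below 0.1% | 1.3% / 1.4% |
| 10% | 0.4% / 0.4% | 8.9% / 12.2% |
| 20% | 9.7% / 11.7% | 45.6% / 63.0% |
| 25% | 22.9% / 28.4% | 65.5% / 83.0% |
| 30% | 40.8% / 50.4% | 80.8% / 93.7% |
| 40% | 76.0% / 86.5% | 96.1% / 99.6% |

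**4. Delay.** On schedule, drug exposure lasts at most about 180 - 21 = 159 days. Adding 14 days of event collection gives 173 days, or 5.68 months. At 26 to 40 patients over 36 months, 5.68 x 26/36 = 4.1 to 5.68 x 40/36 = 6.3 patients may start before an outcome is known.

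**5. Effect on patients treated.** Simulated with that delay, q = 0.20 and L = 0.20. The lower figure acts as soon as the count is reached, the higher at fixed looks.

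- No event prevents transplant: 26.3 falls to 25.5-25.7 at a true rate of 20%, 26.2 to 23.0-23.8 at 30%, and 26.2 to 19.1-20.8 at 40%.
- Every event prevents transplant: about 36 falls to 28-29 at 30%.

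All these falls assume that entry never resumes after a pause, so they are upper limits.

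**The case against.** The strongest reply is that oversight already exists. Every SAE, whatever its attribution, reaches the IND Office within 5 working days; the drug company hears within 24 hours; and SAEs go on to FDA. Under Table 3, resuming after a quickly resolved grade 3 toxicity follows discussion with the sponsor, and 4.2 requires medical-monitor agreement for holds beyond 4 weeks. A reader might infer from the missing rule that this harm could build up with no signal. The documents do not support that: the signals exist and a discretionary review is possible. Slow accrual would be a further signal if other losses were near 40%. What these routes lack is a denominator and a number that makes review mandatory.

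Second, nothing in the documents suggests a high event rate. Section 2 describes a dose taken from phase 1, a drug in phase 3 and mostly mild to moderate events. The only grade 3 or higher events above 10% were anemia or thrombocytopenia (16%), and the proposed count omits uncomplicated myelosuppression. This stands. At a true rate of 20% a 20% limit hardly changes the number treated, and a 10% limit pauses about half of trials or more. The case therefore rests on requiring a review, not on a predicted saving of patients, and the team must choose the limit.

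Third, 4.1.5 allows transplant after an early stop, so discontinuation alone need not cost a patient evaluability. This also stands; the replacement argument covers only death or toxicity that prevents transplant.

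**Conclusion.** The point holds as a cheap improvement, with medium confidence. The supplied text contains no cumulative trigger for reviewing the only investigational drug, and the time-to-event endpoints cannot show harm that occurs before transplant or prevents it. With 20% other loss, the margin to 40 would usually absorb toxicity that blocks transplant in 10% to 30% of patients. With 40% other loss it often would not. All these loss rates are assumptions.

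Two further readings go too far. One is that the plan expressly provides for replacing toxicity losses: Section 6.0 names only donor loss and patient choice, and replacement for toxicity follows from the definition of evaluable. The other is that the rule would reliably spare the numbers of patients simulated above: a pause may be lifted after review, so those are upper limits.

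The appendices and institutional policies were not available. If one already sets a cumulative trigger, citing it in Section 6 would settle the point.

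**What to change.** Add one rule to Section 6 covering all pacritinib-treated patients, transplanted or not.

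- **Count** each patient with (a) pacritinib-related death, (b) permanent discontinuation for pacritinib-related toxicity, or (c) pacritinib-related toxicity that prevents transplant. Related means definitely or possibly related under 8.1.
- **Window:** first dose to the start of conditioning, or to 14 days after the last dose if no transplant follows.
- **Do not count** grade 3 events that resolve under Table 3, uncomplicated myelosuppression, lack of donor, or patient choice.
- **Action:** pause new entry for review by the PI and the IND Office as soon as the boundary is reached among the first 10, 20 or 30 treated. Acting on the running count avoids waiting for patients who stay on drug under 4.1.4.
- **Limit:** the team fixes one before use, from the rate it expects. A 20% limit gives 5/10, 7/20, 10/30; a 10% limit gives 3/10, 5/20, 6/30.

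**Cost.** A short amendment, a running count, and a recorded reason for each permanent discontinuation and each missed transplant. The reasons are needed because expected grade 1-2 events are not captured. In addition, after day 14 only related serious events must be reported, which leaves non-serious toxicity uncovered in the 21 - 14 = 7 days before conditioning. No new committee, procedure or patients are required.

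**Downside.** A possible unneeded pause: 9-12% if the true rate equals the chosen limit, but 23-28% if the limit is 20% and a true rate of 25% would have been acceptable.
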